6.0 RCT STUDY PROCEDURES (AIM 1, R61)

All study activities and interactions may be completed remotely/virtually through a combination of email, phone call, SMS, study app, online assessments, and videoconference. There is no required in-person contact with study staff.

6.1 Study onboarding appointment and baseline assessment

[figure not shown]
All participants will complete an onboarding appointment via phone or HIPAA-compliant videoconferencing platform. Participants will be considered enrolled and be eligible for the enrollment completion incentive once the below activities are complete:

- Informed consent and HIPAA authorization. Receipt of a unique access link to complete their Baseline CASI survey capturing PrEP use history, sexual behaviors, demographics, and determinants of PrEP use (access to care, perceived HIV risk, social support, perceived discrimination, mental health, substance use, and PrEP decision making). The CASI survey is self-administered via secure HIPAA-compliant platform (e.g. RedCap) and participants can complete the survey on their personal device with internet, wi-fi or mobile data. The survey saves after every page thus participants can return to complete the survey if their connection is disrupted or for any other reason.
- Randomized to study condition.
- Receipt of a unique access code and directions to download their free designated version (intervention or control) of the HMP study app from either the Google Play or Apple store.
- Creating their unique HMP account profile and log-in; touring the app features.

The onboarding appointment for intervention participants will also include being connected to their assigned PrEP navigator.

6.2 Participant Enrollment and Onboarding

Figure 2: Participant Enrollment Flow

* Randomization is automated within the study database. Participants are informed of the outcome of randomization as part of their onboarding appointment.

6.3 Intervention Procedures

Intervention arm participants will have access to the three primary intervention components (PrEP Navigation, Digital Health Intervention, and Telehealth PrEP Referral) for the full duration of the 6-month follow-up period, limited to 3-months for a subset of participants enrolled in approximately the final quarter of enrollment. Participants will be encouraged to use the intervention features through a combination of study staff reminders, PrEP navigator interactions, automated in-app notifications, and automated SMS and push notifications.

6.4 Follow-up study assessments

Follow-up study assessments will be conducted for all participants, including standard of care repeat HIV/STI testing³¹ and repeat self-administered CASI survey assessments, with the number of follow-up assessments dictated by timing of enrollment. The baseline questionnaire is distributed after a participant completes informed consent and before they are randomized. If the participant does not complete Informed Consent, HIPAA Authorization, the baseline questionnaire and baseline HIV status verification within 45 days of completing the screening questionnaire, the participant must re-screen to assess eligibility.

The follow-up period (described as the post-randomization phase) begins once participants have been randomized to a study condition. Randomization will occur once participants have connected with study staff for their onboarding appointment. An overview of the pre and post randomization assessments conducted in each study phase are described in Tables 2.1 – 2.3.

A subset of participants will be asked to complete a brief CASI survey pertaining to PrEP uptake and/or persistent use and self-reported STI or HIV testing outcomes at 12-months if this follow-up interval falls within the allowable data collection timeframe based on when a person was enrolled (see Section 17.0 Timeline). The study windows for each follow-up time

Table 2.1: Participant Assessment Timeline

| Pre-Randomization | | | |
|--|----------|-----------|------------------------------|
| Study Activity | Day Open | Day Close | Study Window Duration (days) |
| Screening Questionnaire | 0 | 45 | 45 |
| Informed Consent + HIPAA Authorization | 0 | 45 | 45 |

Table 2.2: Participant Assessment Timeline for Participants Followed 6 -12 Months

| Post-Randomization | | | |
|--|----------|-----------|------------------------------|
| Study Activity | Day Open | Day Close | Study Window Duration (days) |
| App Account Generation | 0 | 0 | 1 |
| Baseline STI Result Abstraction ¹ | 0 | 89 | 89 |
| Baseline HIV Result Abstraction ² | 0 | 45 | 45 |
| 3M Survey | 90 | 165 | 75 |
| 3M DBS | 75 | 165 | 90 |
| 3M HIV/STI Result Abstraction ¹ | 90 | 165 | 75 |
| 6M Survey | 166 | 196 | 30 |
| 6M DBS | 166 | 211 | 45 |
| 6M HIV/STI Result Abstraction ¹ | 166 | 276 | 110 |
| 12M Survey ³ | 365 | 440 | 75 |
| Qualitative Exit Interview ³ | 90 | 276 | 186 |

Table 2.3: Participant Assessment Timeline for Participant Followed for 3 Months

| Post-Randomization | | | |
|--|----------|-----------|------------------------------|
| Study Activity | Day Open | Day Close | Study Window Duration (days) |
| App Account Generation | 0 | 0 | 1 |
| Baseline STI Result Abstraction ¹ | 0 | 89 | 89 |
| Baseline HIV Result Abstraction ² | 0 | 45 | 45 |
| 3M Survey | 90 | 120 | 30 |
| 3M DBS | 75 | 120 | 45 |
| 3M HIV/STI Result Abstraction ¹ | 90 | 165 | 75 |

¹This window represents the dates in which a participant sought HIV/STI testing. The abstraction of such results can occur outside of this window.

²Participants initial eligibility is confirmed via their self-reported HIV negative status captured in the screening questionnaire. Participants are required to have proof of a negative HIV test within 90 days prior to completing the screening questionnaire or within 45 days of completing the screening questionnaire. The window represented in this table indicates that study staff must verify participants HIV negative status within 45 days of the participant completing the screening questionnaire.

³Indicates assessments done for subset of participants

point are intentionally broad to maximize data completeness and accommodate variation in HIV follow-up testing that may occur as part of standard clinical care, PrEP initiation and monitoring, and event-driven HIV testing following a potential exposure event. The target dates for follow-up assessments are at the completion of the 3-month, 6-month, and 12-month mark, with windows before and after these dates to accommodate variation in HIV/STI testing schedules.

For participants that initiate PrEP while on study, study staff will update the timeline for their HIV/STI assessments according to their PrEP initiation date. As HIV/STI testing is expected to be collected as part of their standard PrEP management, we will not ask participants to duplicate this testing at their STI clinic if they can demonstrate having been tested within the acceptable window for their expected 3- or 6-month testing interval. The timeframe in which participants are asked to complete DBS kits and CASI assessments will remain the same, defined by the date participants are randomized.

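### Table 2.3 closes the 3-month survey and blood spot at day 120 for late enrollees, 45 days earlier than for everyone else; a capped close at day 165 would save some primary outcomes at little cost

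*Combined protocol and SAP*

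**What the plan says.** Section 6.4 sets follow-up windows in days from randomization (opening day, closing day, length).

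- Followed 3 months only (Table 2.3): survey "3M Survey | 90 | 120 | 30"; DBS "3M DBS | 75 | 120 | 45". HIV/STI tests sought up to day 165 are accepted for these same people, and footnote 1 adds: "The abstraction of such results can occur outside of this window".
- Followed 6 to 12 months (Table 2.2): survey "3M Survey | 90 | 165 | 75"; DBS "3M DBS | 75 | 165 | 90".

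The text calls the windows "intentionally broad to maximize data completeness" and also ties their width to variation in HIV/STI testing. It gives no reason for the shorter survey and DBS windows in Table 2.3.

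Under section 7.0 and Table 3 footnote 1, uptake needs a self-report (follow-up survey or app) and one verifier (prescription image, drug in DBS, or medical record). Section 3.2.2 describes the control app as timeline, calendar and educational content. Table 3 footnote 7 says that daily in-app medication reporting exists only in the intervention arm.

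**The concern.** The late cohort gets 30 days instead of 75 for the survey, and 45 instead of 90 for the DBS. Someone who would answer between days 121 and 165 counts if enrolled early and is out of window if enrolled late.

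The survey matters more than the DBS. The app, image and record routes are described as ways to show that a person started PrEP. At the planning rates (2.5% in control, 10% with the 7.5-point effect) most participants do not start, and no route other than the survey is described for confirming that. Nor is there a rule that counts a missing survey as no start: section 9.2 sends missing data to weighting or imputation if bias is suspected. Because the control app lists no tracker, a missed survey may cost the two arms different information.

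At stake are some precision on the primary comparison, which also decides milestone 5, and possible bias if slow responders differ in uptake. Section 9.1 allows for 10% missing data at month 3 without distinguishing this cohort.

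**Working it through.** **Inputs from the documents.** N = 336, 1:1, 21 months of enrollment, two-sided 5% chi-square test, 2.5% vs 10.0%, 10% missing (section 9.1, Table 4 note). The late cohort is about the last 3 months of enrollment (section 3.0) or the final quarter (section 3.2).

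**Window gap.** 165 − 120 = 45 days for both survey and DBS. The lengths printed in these rows agree with closing day minus opening day.

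**Plan's own figure.** With 10% missing, 336 × 0.90 / 2 = 151 per arm. Enumerating the Pearson chi-square test exactly gives 79.7% power, which matches the stated 80%. The pooled normal approximation gives 77.1% at 151 per arm, and 81.3% at 168 per arm with no missing data.

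**Size of the late cohort.** With uniform accrual, 336 × 3/21 = 48. If the final quarter means one fourth, 336 × 0.25 = 84.

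**Response by day 120 (assumed).** Suppose 90% respond when given the full 75 days, with a Weibull time to response of shape k. The share responding in the first 30 days is 1 − exp(−ln 10 × (30/75)^k).

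| k | Responding by day 120 | Lost of 48 | Lost of 84 |
|---|---|---|---|
| 1 (constant rate) | 60.2% | 14.3 | 25.0 |
| 0.5 | 76.7% | 6.4 | 11.2 |
| 0.25 (strongly front-loaded) | 84.0% | 2.9 | 5.1 |

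Lost = cohort size × (0.90 − share responding by day 120).

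**Effect on missingness and exact power.**

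- Smallest loss: (302.4 − 2.9)/2 = 149.8, about 150 per arm. Missing 10.9%, power 79.4%.
- Largest loss: (302.4 − 25.0)/2 = 138.7, about 139 per arm. Missing 17.4%, power 76.2%.

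**Second assumption as a check.** If 5% to 30% of the late cohort would respond only on days 121 to 165, the loss is 48 × 0.05 = 2.4 to 84 × 0.30 = 25.2 outcomes. Pooled power falls from 77.1% to between 76.8% and 73.5%. The order of magnitude is the same.

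Both calculations treat every late non-response as a lost outcome. Any person whose status is established through the app with an image or record reduces the loss.

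**The case against.** Five points deserve weight.

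1. *Other routes exist.* A reader might infer that the survey and DBS alone decide the outcome. They do not: an app report with a prescription image or medical record also meets it, and a missing DBS alone need not lose anything. Table 3 footnote 5 even mentions in-app reporting of a PrEP start, for those reaching 12 months, without limiting it by arm. What remains is the non-starters, and the unclear control-arm app route.
2. *No contradiction.* A reader might set the day-120 close against the stated aim of broad windows. That sentence goes on to HIV follow-up testing, which explains why test windows are longer. The 30- and 45-day lengths also equal those of the 6-month survey and DBS in Table 2.2, so they may be a deliberate close-out choice. The text is consistent, but it does not justify the shorter window.
3. *Timeline.* A reader might infer from the HIV/STI window that recovery to day 165 fits the existing schedule. That is not established. Those results come from routine-care records, whereas a survey needs participant contact and a kit needs mailing, batch shipping and assay. The last day of R61 survey and DBS collection is not stated. A cap at that day answers this: it adds no study time, and it helps only those for whom time remains.
4. *Late answers may pick up late starts.* This stands. A DBS result is undated, and section 9.2.1 does not say that a start is assigned by date of first dose. Table 2.2 already has the same exposure to day 165, so the rule is needed in any case. The first-dose date is already used for the PrEP-use measure (Table 3 footnote 2).
5. *Assumed curves.* Also correct. Reminders and incentives may bring responses forward, and the low end of the range, 0.3 points of power, is negligible.

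**Conclusion.** The shorter window is real and unexplained, and for the late cohort it discards survey and DBS responses that Table 2.2 would accept. The likely cost is modest: about 3 to 25 of 336 primary outcomes, and 0.3 to 3.5 points of exact power (79.7% to between 79.4% and 76.2%). This rests on a late cohort of 48 to 84, 90% response in a 75-day window, the assumed response curves, and no rescue through the app route. Any bias, including a difference between arms, is possible but cannot be sized from the documents. The point stands as an inexpensive improvement; the outcome remains obtainable without it.

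A minor related point concerns secondary outcomes only. At 6 months the survey row is "6M Survey | 166 | 196 | 30" and the DBS row "6M DBS | 166 | 211 | 45", so a kit returned on days 197 to 211 may arrive after the survey that would supply the self-report has closed.

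**What to change.** In Table 2.3, close the 3M Survey and 3M DBS at *day 165 or the last day of R61 survey and DBS collection, whichever comes first*. In section 9.2.1, state that a start counts towards the 3-month outcome by its reported or recorded first-dose date, not by the date of the survey or DBS. Also state whether control participants can report a PrEP start in the app. If day 120 is kept, give the reason.

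The cost is two table entries, one sentence on dating, and reminder settings; no procedure or study time is added. The downside is a wider spread of survey dates and longer recall in the late cohort, as Table 2.2 already accepts for earlier enrollees. The last people enrolled may still have to close at day 120.

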6.5 Self-collected blood sample

Dependent on their enrollment date, participants will be asked to complete one to two self-collection whole blood sample kits corresponding to a 3- and 6-month follow-up to assess for PrEP uptake by measuring for the presence and levels of tenofovir diphosphate and emtricitabine triphosphate (TFV-DP/FTC-TP) or Cabotegravir (CAB) levels. Participants may have the specimen collection kits sent to their current residence or any mailing address of their choice. Kits will contain detailed instructions for use of the blood collection device as well as all packaging materials needed to return the kit to the lab. See Section 16.1 for laboratory details.

6.6 Clinic assessments

We will conduct assessments of all participating clinics to evaluate staffing, patient volume, hours of operation, and available services. These assessments may be conducted using a combination of in-person and remote/virtual interactions and will occur within 3-months before or after initiating patient participant recruitment at each site, and again within 3-months before or after the end of the study follow-up period (see Section 17.0). Additionally, we will track how clinics are engaging with technical assistance services as offered through NC HTEC.

Alongside in-depth interviews (Section 6.7), we will also ask relevant stakeholders about intervention acceptability and organizational factors that may influence PrEP provision and integration of services, including organizational readiness for change, support climate, and intervention-values fit ³⁹⁻⁴¹. As part of anticipated biannual convening of study leadership, state policymakers, and members of our Community Advisory Board, we will monitor relevant policy changes such as those pertaining to insurance, PrEP coverage, or recommendations for use that may serve as external influences relevant to our observed outcomes. This information will be documented in study minutes and circulated to all attendees.

6.7 Qualitative in-depth interviews

A sub-set of up to 50 participants will complete an in-depth interview following their 3 or 6-month study visit to provide contextualized data about: experience with the study participation, perceived accessibility of PrEP before and after study enrollment, evaluation of the acceptability of this PrEP-access model, unmet PrEP-related health service needs/barriers, experience initiating PrEP (if relevant), experience using the study-related intervention components (app, PrEP navigator, telehealth for PrEP) (if relevant), and other emergent topics as raised by participants. Participant interviews may be conducted remotely by phone or videoconference platform.

Up to 50 relevant stakeholders, including STI clinic staff, healthcare providers, and other stakeholders relevant for PrEP services will also complete in-depth interviews covering topics such as: experiences and challenges with

being part of a participating clinic for this study, perceived accessibility of PrEP to target patient population before and after study implementation, perceived strengths and drawbacks of this PrEP-access model, suggested changes to this PrEP-access model, unmet PrEP-related health service needs/barriers among target patient population, and other emergent topics as raised by participants. Stakeholder interviews may be conducted in-person or remotely by phone or videoconference platform.

Interviews will be conducted by trained research staff experienced in qualitative research. Interviews will be guided by the use of an SOP and a semi-structured interview guide which will include open-ended questions corresponding to each qualitative endpoint. Interviewers will be allowed the flexibility to probe patient responses and pursue discussion diverging from the initial interview questions if it is relevant to the endpoints of interest. Each interview will be digitally recorded and transcribed to text for analysis.

7.0 OUTCOME MEASURES AND DATA SOURCES

For interventions that address systems-level challenges or utilize patient navigation as an intervention component, PrEP uptake is an appropriate primary outcome as it is an indication of the success of the intervention to overcome the barriers to access to the health service/treatment^{42,43}. Given the current lack of PrEP availability in the proposed study settings, an intervention that can overcome the multi-level barriers to PrEP access and uptake is a critical first-step.

With PrEP uptake as the primary outcome and the primary objective to increase PrEP uptake, this study will follow a similar operational definition as another large-scale mHealth RCT intervention for PrEP uptake among MSM in the southern United States⁴⁴: self-report taking any PrEP (oral or injection) on a follow-up survey or in the app, AND verified by at least one of the following: (1) an uploaded photo or image demonstrating a PrEP prescription; OR (2) any indication of the presence of tenofovir diphosphate or cabotegravir in DBS; OR (3) staff-abstracted electronic medical record of PrEP prescription issued or physician notation of PrEP initiated.

Table 3 presents the study Outcome Measures and their data sources.

| Table 3: Study Outcome Measures and Data Sources | | | |
|--|---------------------------------------|---|---|
| Name | Time Frame | Brief Description | Data sources |
| Primary outcome | | | |
| PrEP uptake | 3-month follow-up | Verified self-reported PrEP use (first dose, oral or injectable) ¹ | CASI, in-app report, EHR abstraction, self-collected lab sample |
| Secondary outcomes | | | |
| PrEP uptake | 6-month follow-up ⁴ | Verified self-reported PrEP use (first dose, oral or injectable) ¹ | CASI, in-app report, EHR abstraction, self-collected lab sample |
| PrEP care engagement | 3- and 6-month ⁴ follow-up | Daily oral or event driven PrEP: after PrEP uptake, number and dates of any subsequent PrEP visits or new/refilled | CASI, EHR |

| | | | |
|--|--|--|--|
| | | PrEP prescriptions Injectable PrEP : after initial injection, number and dates of any subsequent PrEP visits/injections | |
| PrEP use | 3- and 6-month ⁴ follow-up | Number of consecutive months PrEP used, based on date of first and last dose ² | CASI, EHR |
| PrEP adherence (self-report) | 3- and 6-month ⁴ follow-up | Daily oral PrEP : reported PrEP use (past 30 days) Event-driven PrEP : reported PrEP use corresponding to reported sexual activity (past 30 days) Injectable PrEP : based on date of injections | CASI |
| PrEP adherence (injection history & drug measurement) | 3- and 6-month ⁴ follow-up | Daily oral PrEP : PrEP concentrations detected at designated study follow-up visits, based on intraerythrocytic TFV-DP collected as DBS; Injectable PrEP : based on dates of injections | Self-collected lab sample, EHR |
| Incident STI/HIV | 3- and 6-month ⁴ follow-up | Clinical test result (yes / no / indeterminate / missing) for each STI and HIV that participant is tested for. | CASI; State, clinic, commercial lab results ³ |
| PrEP Stigma | 3- and 6-month ⁴ follow-up | Self-reported scored PrEP Stigma scale | CASI |
| Implementation measures (intervention arm and stakeholders) | | | |
| Fidelity-Engaged by PrEP navigator | First two weeks following enrollment | Proportion of Intervention Arm enrolled participants that are engaged by the PrEP navigator within two weeks of enrollment | Intervention CRF |
| Intervention satisfaction - Quantitative | 3- and 6-month ⁴ follow-up | Average score on participant-completed System Usability Scale (10 item universal measure of usability and acceptability). | CASI |
| Intervention satisfaction – Qualitative | 3- or 6-month ⁴ follow-up | Description of participant experiences and satisfaction, usefulness and attribution to PrEP use while on study and with each intervention component. | In-depth interviews with participants |
| Acceptability | Within 3-months before or after baseline and | Description of stakeholder experiences and acceptability of intervention, readiness for change, implementation | In-depth interviews and surveys with |

| | | | |
|--------------------------------|--|--|--|
| | within 3 months before or after study close-out | climate, and intervention values | stakeholders |
| Clinic measures | | | |
| STI service delivery | Baseline, 3- and 6-month ⁴ follow-up | Proportion of enrolled participants receiving STI screening (urogenital, rectal, pharyngeal) at baseline (pre-enrollment) and follow-up timepoints | State, clinic, commercial lab results ³ |
| Sexual health service delivery | Within 3-months before or after baseline and within 3 months before or after study close-out | New or modified sexual health programs or offerings at participating clinic, including PrEP (on-site or integrated into clinic), point-of-care testing, and other initiatives | In-depth interviews and surveys with stakeholders |
| Exploratory measures | | | |
| PrEP uptake | 12-month follow-up ⁵ | Verified self-reported PrEP use (first dose, oral or injectable) ⁶ | CASI, in-app report, EHR abstraction |
| PrEP care engagement | 12-month follow-up ⁵ | Daily oral or event driven PrEP : after PrEP uptake, number and dates of any subsequent PrEP visits or new/refilled PrEP prescriptions Injectable PrEP : after initial injection, number and dates of any subsequent PrEP visits/injections | CASI, EHR |
| PrEP use | 12-month follow-up ⁵ | Number of consecutive months PrEP used, based on date of first and last dose ² | CASI, EHR |
| PrEP adherence (self-report) | 12-month follow-up ⁵ | Daily oral PrEP : reported PrEP use (past 30 days) Event-driven PrEP : reported PrEP use corresponding to reported sexual activity (past 30 days) Injectable PrEP : based on date of injections | CASI |
| Incident STI/HIV | 12-month follow-up ⁵ | Clinical test result (yes / no / indeterminate / missing) for each STI and HIV that participant is tested for. | CASI; State, clinic, commercial lab results ³ |
| Effective HIV protection | First 3 months of trial | Proportion of days out of the first 3 months of the trial that participant was "effectively" protected from HIV transmission based on their self-reported PrEP use and self-reported | CASI, in-app reported behaviors ⁷ |

| | | | |
|--------------------------|-----------------------------------|---|--|
| | | sexual behavior. | |
| Effective HIV protection | 6-month study period ⁴ | Proportion of total days of the trial that participant was "effectively" protected from HIV transmission based on their self-reported daily PrEP use and self-reported sexual behavior. | CASI, in-app reported behaviors ⁷ |

¹ Persons who self-report taking any PrEP (oral or injection) during a follow-up survey OR in their app will meet this endpoint if this self-report is verified by at least one of the following: (1) an uploaded photo or image demonstrating a PrEP prescription; OR (2) any indication of the presence of tenofovir diphosphate or cabotegravir in DBS; OR (3) staff-abstracted electronic health record of PrEP prescription issued or physician notation of PrEP initiated.

² First dose and last dose determined based on self-report for oral PrEP and medical record (or self-report if record not available) for injectable PrEP. Respondents endorsing any PrEP dose will have uploaded current PrEP prescription as described in PrEP uptake outcome as above.

³ State, clinic and commercial labs: We will collect HIV/STI test results directly from laboratory portals or via secure upload of results from participants or participating clinics' medical records.

⁴ Participants who reach 6-months of study follow-up prior to study end will contribute to 6-month outcome measures.

⁵ Participants who reach 12-months of follow-up prior to study end (see 17.0 Timeline) will complete a brief CASI survey inquiring about PrEP use, including PrEP uptake and any interruptions or discontinuations of PrEP. They will also maintain ability to self-report PrEP start within the app through month 12. Self-reported STI and HIV results will also be captured at this time point, as well as preferences for provision of extended PrEP navigation resources.

⁶ Persons who self-report taking any PrEP (oral or injection) during a follow-up survey OR in their app will meet this endpoint if this self-report is verified by at least one of the following: (1) an uploaded photo or image demonstrating a PrEP prescription; OR (2) staff-abstracted electronic health record of PrEP prescription issued or physician notation of PrEP initiated. DBS samples will not be collected at month 12.

⁷ All participants (intervention and control) will be asked questions on CASI about PrEP use, medication adherence and sexual behavior; CASI data will be used to calculate an estimate of effective protection for **all** participants. In-app daily medication adherence self-report and daily sexual behavior self-report are only available for intervention arm participants; in-app data will be used to calculate an app-based estimate of effective protection for any **intervention arm** participants who used the app to record these behaviors.

